Appendix B List of commonly used asthma controller therapies

ICS	ICS/LABA	LABA	Anti-leukotrienes	Long-acting muscarinic antagonist (LAMA)	Methylanthines
Beclomethasone dipropionate CFC	Fluticasone Propionate / Salmeterol	Salmeterol Formoterol	Montelukast Pranlukast	Tiotropium Glucopyrronium bromide	Aminophylline Theophylline
Beclomethasone dipropionate HFA	Fluticasone Propionate / Formoterol	Bambuterol Clenbuterol	Zafirlukast Zileuton	Acidinium bromide Umeclidinium	Dyphylline Oxtryphylline
Budesonide DPI	Fluticasone Furoate / Vilanterol	Tulobuterol Vilanterol			Diprophylline Acebrophylline
Budesonide HFA	Budesonide /Formoterol	Olodaterol			Bamifylline
Budesonide nebulas	Mometasone Furoate / Formoterol	Indacaterol			Doxofylline
Ciclesonide HFA					
Flunisolide HFA					
Fluticasone propionate HFA	Beclometasone Dipropionate and Formoterol				
Fluticasone propionate DPI					
Mometasone furoate					
Triamcinolone acetonide					
Fluticasone furoate					

Appendix C Low, medium and high dose inhaled corticosteroids- Children (6-11 years)

Inhaled Corticosteroid	Total Daily Dose (mcg)		
	Low	Medium	High
Beclometasone dipropionate (CFC)	100–200	>200–400	>400
Beclometasone dipropionate (HFA)	50–100	>100–200	>200
Budesonide (DPI)	100–200	>200–400	>400
Budesonide (HFA)	100–200	>200–400	>400
Budesonide (nebulized)	250–500	>500–1000	>1000
Ciclesonide (HFA)	80	>80–160	>160
Flunisolide (HFA)	160	>160–<320	320
Fluticasone propionate (DPI)	100–200	>200–400	>400
Fluticasone propionate (HFA)	100–200	>200–500	>500
Mometasone furoate	110	≥220–<440	≥440
Triamcinolone acetonide	400–800	>800–1200	>1200

CFC = chlorofluorocarbon propellant; DPI = dry powder inhaler; HFA = hydrofluoroalkane propellant; nebulized = nebulized solution
Source: Adapted from Global Initiative for Asthma (GINA) 2015 guidelines with the addition of Budesonide HFA and Flunisolide information

Appendix D Handling of missing data

Annualized severe exacerbation events during the 52-Week period

- ***Pattern mixture model (PMM)***

Step 1. The 52-week observation period is partitioned into monthly (4-week) segments. In the analysis, for each patient, in each month, an imputation flag (impute_{fl}) will indicate whether the patient needs imputation in that month.

Step 2. *Calculation of observed monthly mean of event count*

Within each month, the logistic regression model will be fitted to the observed data to model coefficient estimates and the estimated variance-covariance matrix, with adjusting for the planned treatment group, age, baseline weight (≤ 30 kg, > 30 kg), region (pooled country), baseline eosinophil level (removed for the baseline eosinophils ≥ 0.3 Giga/L population), baseline FeNO level, baseline ICS dose level, and number of severe exacerbation events within 1 year prior to the study. From the posterior distribution of the model coefficients, we randomly draw 40 sets of iid samples. As a result, for each patient and in each month, 40 estimated probabilities can be obtained by using the 40 samples of coefficients and the patient's covariates values.

Step 3. *Imputation of event count after study withdrawal*

If a patient withdraws from the study at the k th ($1 \leq k < 28$) day of Month i prior to Week 52, and experienced a severe exacerbation within the first k days, this patient will be considered as “observed” (impute_{fl}=0) up to Month i and will need imputations (impute_{fl}=1) from Month $i+1$ to Month 13 (Week 52).

If a patient withdraws from the study at the k th ($1 \leq k < 28$) day of Month i prior to Week 52, and has no severe exacerbation in Month i , this patient will be considered as “observed” (impute_{fl}=0) up to Month $i-1$ and will need imputations (impute_{fl}=1) from Month i to Month 13 (Week 52).

For a patient who needs imputation from Month $i+1$ to Month 13, in each month, 40 independent random samples will be respectively drawn from 40 estimated Bernoulli distributions, whose probabilities are obtained in Step 2. For each patient who early withdraws from the study, 40 sets of complete event count data can be obtained by summing the observed event count prior to withdrawal and each series of imputed binary events after withdrawal up to Week 52.

Step 2 and 3 can be realized by using PROC MI in SAS. Sample code can be found below:

```
proc mi data=dd seed=9816388 nimpute=40 out=outdata;  
by month;  
class outcome trt01pn weight eosbgp1n cntygr1 icsgrp fenoblgrn ;  
monotone reg (asmanum/details)  
logistic (outcome=trt01pn age weight eosbgp1n cntygr1 icsgrp fenoblgrn asmanum/details  
DESCENDING);  
var eosbgp1n cntygr1 age icsgrp trt01pn fenoblgrn asmanum outcome;  
run;
```

Step 4. A negative binomial model with the same set of covariates as in the primary endpoint analysis will be fitted with 40 sets of complete datasets obtained in Step 3, so as to obtain 40 sets of treatment effect estimates and p-values accordingly. Log transformed observation duration will be the offset variable for patients who complete the 52-Week treatment/study period, and log transformed 52 weeks will be the offset variable for patients who discontinue the study before Visit 18 (Week 52). At last, the SAS MIANALYZE procedure will be used to generate statistical inferences by combining results from the 40 analyses using Rubin's formula.

Step 4 can be realized by using PROC MIANALYZE in SAS. Sample code can be found below

```
proc mianalyze data=rr_conv;  
by Label;  
modeleffects Estimate;  
stderr StdErr;  
ods output ParameterEstimates=rr_pooled;  
run;  
proc mianalyze data=aer_conv;  
by TRT01PN;  
modeleffects Estimate;  
stderr;  
ods output ParameterEstimates=aer_pooled;  
run;
```

- **Control-based PMM**

All steps are the same as the aforementioned approach except in **Step 2**: the individual monthly mean probability will be calculated based on observations in placebo arm only, with adjustment of missing observation duration.

- **Tipping point analysis**

The tipping point analysis for severe exacerbation events will use the similar approach as PMM-MI with tipping values for the odds

Step 1. Estimation for the monthly binary event probability using observed data

Within each month up to Week 52, the logistic regression model will be fitted to the observed data to obtain the model coefficient estimates and the estimated variance covariance matrix, with adjusting for the planned treatment group, age, baseline weight (≤ 30 kg, >30 kg), region (pooled country), baseline eosinophil level (removed for the baseline eosinophils ≥ 0.3 Giga/L population), baseline FeNO level, baseline ICS dose level, and number of severe exacerbation events within 1 year prior to the study. From the posterior distribution for the model coefficients, we randomly draw 40 sets of iid samples. As a result, for each patient and in each month, 40 estimated binary event probabilities can be obtained by using the 40 samples of coefficients and the patient's covariate values.

Step 2. Tip on the monthly binary odds (the probability of have an event in the month over the probability of being event-free in the month)

Within each month, for the patients from the placebo group(s) and need imputation in that month, the estimated odds for binary event will be deflated by decreasing a positive amount; for the patients from the treatment group(s) and need imputation in that month, the estimated odds for binary event will be inflated by increasing a positive amount. After the deflation/inflation, 40 sets of binary event probabilities can be obtained for the placebo and treatment groups, respectively.

Step 3. Multiple Imputation of binary event by month after study withdrawal

For a patient who needs imputation from Month $i+1$ to Month 13, in each month, 40 independent random samples will be respectively drawn from 40 estimated Bernoulli distributions, whose probabilities are obtained in Step 2.

For each patient who early withdraws from the study, 40 sets of complete event count data can be obtained by summing the observed event count prior to withdrawal and each series of imputed binary events after withdrawal up to Week 52.

Step 4. A negative binomial model with the same set of covariates as in the primary analysis will be fitted to the 40 sets of complete datasets obtained in Step 3, so as to obtain 40 sets of treatment effect estimates and p-values accordingly. Log transformed observation duration will be the offset variable for patients who complete the 52-Week treatment/study period, and log transformed 52 weeks will be the offset variable for patients who discontinue the study before Visit 18 (Week 52). Then, the SAS MIANALYZE procedure will be used to generate statistical inferences by combining results from the 40 analyses using Rubin's formula.

Step 2, 3 and 4 will be repeated iteratively until the p-value for combined treatment effect of dupilumab compared to placebo estimated in Step 4 is >0.05 .

Change from baseline in % predicted pre-BD FEV1 at Week 12

Pattern mixture model-multiple imputation (PMM-MI)

Step 1. Monotone missing pattern was induced by Markov Chain Monte Carlo (MCMC) method using PROC MI: for patients who have missing values at intermediate visits, but have value at subsequent visits, the intermediate missing values were imputed assuming a multivariate normal distribution over observations from all visits. 40 datasets with a monotone missing pattern will be obtained using this method.

Step2. For each of the imputed dataset with monotone missing pattern obtained in Step 1, the remaining missing data will be imputed using the regression method for the monotone pattern with adjustment for covariates including response variable, treatment groups, baseline weight ($\leq 30\text{kg}$, $>30\text{kg}$), region (pooled country), ethnicity, baseline eosinophil level (removed for the baseline eosinophils ≥ 0.3 Giga/L population), baseline FeNO level, baseline ICS dose level, and baseline % predicted pre-BD FEV1 and missing pattern defined by reason of treatment discontinuation. All available data in the monotone missing pattern data will be used. 40 fully imputed datasets are obtained.

Step 3. Each of the 40 complete datasets will be analyzed using an ANCOVA model with change from baseline in % predicted pre-BD FEV1 at Week 12 as the response variable, treatment, baseline weight ($\leq 30\text{kg}$, $>30\text{kg}$), region (pooled country), ethnicity, baseline eosinophil level (removed for the baseline eosinophils ≥ 0.3 Giga/L population), baseline FeNO level, baseline ICS dose level, and baseline % predicted pre-BD FEV1 value as covariates. Then the SAS MIANALYZE procedure will be used to generate statistical inferences by combining results from the 40 analyses using Rubin's formula.

Control based PMM-MI

The analysis is similar as the standard PMM-MI described above, except **Step 2**. To implement control-based imputation, we broke the imputation process into a sequence of PROC MI, where each call is to impute missing values at one time-point only. The steps are as follows:

Step 2.1 Call PROC MI to impute values for the first time-point t with missing values. The input dataset include data up to time-point t for all Placebo patients and patients on Dupilumab with missing values at time-point t .

Step 2.2 Repeat Step 2.1 for all the following time-points sequentially. Data imputed in the previous step will be included for imputation of missing values at time-point $t+1$.

Tiping point analysis

Step 1. 40 imputations will be performed to generate 40 completed data sets following Step 1 and 2 for PMM-MI.

Step 2. The imputed % predicted FEV₁ values in Dupilumab group are subtracted by a positive amount d for each imputed data sets.

[figure not shown]
Step 3. The imputed % predicted FEV₁ values in placebo group are added by a positive amount p for each imputed data sets.

Step 4. Change from baseline in % predicted pre-BD FEV₁ will be analyzed using the ANCOVA model as described in the PMM-MI for each of the 40 complete datasets. Then the SAS MIANALYZE procedure will be used to generate statistical inferences by combining results from the 40 analyses using Rubin's formula.

Step 2 and Step 3 will be repeated iteratively until the p-value for treatment effect of dupilumab compared to placebo estimated in Step 4 is >0.05 .

[figure not shown]
Appendix E Asthma Control Questionnaire-Interviewer Administered (ACQ-IA) for Children 6 to <12 years

[figure not shown]
Asthma Control Questionnaire, 7-question version (ACQ-7)

[figure not shown]
© The Asthma Control Questionnaire: Interviewer-Administered (ACQ-IA) is copyrighted and all rights are reserved. No part of this questionnaire may be sold, modified or reproduced without the express permission of Elizabeth Juniper on behalf of QOL Technologies Ltd

JULY 2011

[figure not shown]

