1.5 MODIFICATIONS TO THE STATISTICAL SECTION OF THE PROTOCOL

This section summarizes major changes to the protocol statistical section with emphasis on changes after study start (after the first patient was enrolled) but before the study is unblinded.

The protocol history table below gives the timing, rationale, and key details of major changes to the protocol statistical section.

Table 1 - Protocol amendment statistical changes

Amendment Number	Date Approved	Rationale	Description of statistical changes
2	31-May-2018		
The following text:
 
The sample size of this study was based on a comparison between dupilumab versus placebo with regard to the primary endpoints of annualized rate of severe exacerbations at Week 52. Assuming the number of severe exacerbations follows a negative binomial distribution with a dispersion parameter of 1.5, a placebo annualized rate of exacerbations being 1.0, a randomization ratio of 2:1, with 294 randomized patients (196 for dupilumab and 98 for matching placebo group), the study will have approximately 90% power to detect a 50% relative risk reduction (ie, annualized rate of 0.5 for the dupilumab group) in the annualized rate of severe exacerbations at the 2-tailed significance level of $\alpha=0.05$. This calculation assumes a linear discontinuation rate (20% at 1 year), thus the average exposure duration for patients is 0.9 year.
 
Was replaced with:
 
The sample size of this study was based on a comparison between dupilumab versus placebo with regard to the primary endpoints of annualized rate of severe exacerbations at Week 52. [REDACTED]
 
[REDACTED]
 
[REDACTED]
 
[REDACTED]
 
[REDACTED]
 
[REDACTED]
 
[REDACTED]
 
[REDACTED]
 
[REDACTED]
 
[REDACTED]
 
[REDACTED] This calculation also assumes a linear discontinuation rate (20% at 1 year), thus the average exposure duration for patients is 0.9 year.

3	18-October-2019		
The following text was added:
 
The sample size of this study was based on a comparison between dupilumab versus placebo with regard to the primary endpoints of annualized rate of severe exacerbations at Week 52. [REDACTED]
 
[REDACTED]
 
[REDACTED]
 
[REDACTED]

Amendment Number	Date Approved	Rationale	Description of statistical changes

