2.4.4.4 Multiplicity issues

To control the type-I error rate for the analysis of efficacy endpoint, a hierarchical testing procedure will be applied at a 2-sided 5% significant level, ie, each hypothesis will be formally tested only if the preceding one is significant at the 2-sided 5% level.

To match the approved indication in adults and adolescents, for the US and US reference countries, the testing hierarchy will start with baseline blood eosinophils ≥ 0.3 Giga/L population. For EU and EU reference countries, the testing hierarchy will start with Type 2 inflammatory asthma phenotype population. The complete list of the endpoints with their testing order is specified in [Table 9](#) (For US and US reference countries) and [Table 10](#) (for EU and EU reference countries).

For US and US reference countries:

Table 9 - Hierarchical testing order for US and US reference countries:

Endpoints	Population	Test Order
Annualized rate of severe exacerbation events during the 52-week placebo-controlled treatment period	Patients with baseline blood eosinophils ≥ 0.3 Giga/L	1 st
Annualized rate of severe exacerbation events during the 52-week placebo-controlled treatment period	Patients with baseline blood eosinophils ≥ 0.15 Giga/L	2 nd
Annualized rate of severe exacerbation events during the 52-week placebo-controlled treatment period	Type 2 inflammatory asthma phenotype (Baseline blood eosinophils ≥ 0.15 Giga/L or Baseline FeNO ≥ 20 ppb)	3 rd
Change from baseline in pre-bronchodilator % predicted FEV1 at Week 12.	Patients with baseline blood eosinophils ≥ 0.3 Giga/L	4 th
Change from baseline in pre-bronchodilator % predicted FEV1 at Week 12.	Patients with baseline blood eosinophils ≥ 0.15 Giga/L	5 th
Change from baseline in pre-bronchodilator % predicted FEV1 at Week 12.	Type 2 inflammatory asthma phenotype (Baseline blood eosinophils ≥ 0.15 Giga/L or Baseline FeNO ≥ 20 ppb)	6 th
Change in ACQ-7-IA at Week 24	Patients with baseline blood eosinophils ≥ 0.3 Giga/L	7 th
Change in ACQ-7-IA at Week 24	Patients with baseline blood eosinophils ≥ 0.15 Giga/L	8 th
Change in ACQ-7-IA at Week 24	Type 2 inflammatory asthma phenotype (Baseline blood eosinophils ≥ 0.15 Giga/L or Baseline FeNO ≥ 20 ppb)	9 th
Annualized rate of severe exacerbation events during the 52-week placebo-controlled treatment period	Baseline FeNO ≥ 20 ppb	10 th
Change from baseline in pre-bronchodilator % predicted FEV1 at Week 12	Baseline FeNO ≥ 20 ppb	11 th

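### Imputation of missing severe exacerbations ignores each child's own on-study events: the pattern-mixture and tipping-point standard errors come out a few percent too small, and the rate ratio is biased if withdrawal follows exacerbations

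*SAP*

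**What the plan says.** SAP section 2.4.4.1 plans three missing-data analyses to test the robustness of the primary conclusion: a pattern mixture model (PMM), a control-based PMM and a tipping-point analysis. Appendix D gives the rules.

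- **Step 2** fits a separate logistic model in each 4-week month. The covariates are planned treatment, age, weight, region, eosinophil level, "baseline FeNO level, baseline ICS dose level, and number of severe exacerbation events within 1 year prior to the study".
- **Step 3** states that for each missing month "40 independent random samples will be respectively drawn from 40 estimated Bernoulli distributions". The sample code runs by month and its outcome model is "logistic (outcome=trt01pn age weight eosbgp1n cntygr1 icsgrp fenoblgrn asmanum/details".
- On-study events are added to the imputed ones afterwards. An event in the month of withdrawal also decides whether imputation starts in that month or the next. They have no other role.
- **Step 4** fits the primary negative binomial model to the completed counts.
- The control-based version changes only Step 2, to placebo-based probabilities. The tipping-point version uses the same monthly models and shifts the odds.

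The FEV1 imputation in the same appendix works differently. It conditions on earlier visits: "All available data in the monotone missing pattern data will be used". The primary analysis (section 2.4.4.1) uses observed events and follow-up time and imputes nothing.

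**The concern.** A negative binomial model says that children differ in underlying rate beyond their covariates. A child's own on-study count is then informative about that child's later months, and the primary likelihood uses it. The imputation step discards it and assumes that withdrawal is unrelated to on-study events once baseline covariates are known, which is a stronger assumption than the primary analysis makes. Two consequences follow:

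- Independent draws remove between-child variation from the imputed part, so the completed data look less dispersed than they should and the standard error shrinks.
- If children tend to leave after exacerbating, they are given average rates for their covariates and the rate ratio moves.

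At stake is the credibility of the planned robustness evidence for the primary endpoint. The primary p-value is not at stake.

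**Working it through.** **Inputs.** The current rates and dispersion are redacted. The only unredacted set is the superseded calculation in SAP section 1.5: "negative binomial distribution with a dispersion parameter of 1.5, a placebo annualized rate of exacerbations being 1.0, a randomization ratio of 2:1", with 294 children (196 and 98). Section 1.3 gives 20% linear discontinuation at 1 year and 0.9 year mean exposure. Section 1.1 gives about 345 children in the type 2 population, which is 230 and 115 at 2:1. Section 2.4.4.4 sets the level: "a hierarchical testing procedure will be applied at a 2-sided 5% significant level".

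**Reproducing the plan's figure.** Var(log RR) = [1/(tμ₀)+k]/n₀ + [1/(tμ₁)+k]/n₁ = (1.111+1.5)/98 + (2.222+1.5)/196 = 0.0456, so SE = 0.2136. Then 0.6931/0.2136 − 1.96 = 1.285, which is 90.06% power. This matches "the study will have approximately 90% power to detect a 50% relative risk reduction".

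**Later rate given own history.** Under a negative binomial model, the expected rate after y events in time t is μ(1+ky)/(1+kμt). For a placebo child leaving at t = 0.5 with μ = 1 and k = 1.5, the denominator is 1.75:

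- y = 0: 1/1.75 = 0.57 per year
- y = 1: 2.5/1.75 = 1.43
- y = 2: 4/1.75 = 2.29
- y = 3: 5.5/1.75 = 3.14

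From y = 0 to y = 3 the range is 0.80 to 2.00 at k = 0.5, and 0.44 to 3.78 at k = 2.5. Appendix D gives all of these children about 1.0 when their baseline covariates match.

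**Standard error.** This was simulated with 2,000 to 2,500 trials per scenario, 230 against 115 children, gamma frailty, 13 monthly yes/no outcomes, 20 imputations (the SAP plans 40) and Rubin's rules. Models contained treatment only, so the dispersion stands for what remains after covariates. The one-event-per-month limit moves the complete-data rate ratio from 0.50 to about 0.52 to 0.53.

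Base case (k = 1.5, 20% withdrawal unrelated to outcome):

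- The PMM mean SE is 0.1835 against its own sampling SD of 0.1926, a ratio of 0.95, with coverage 93.6%.
- For comparison, the primary model's SE is 0.1926 and the SE with no missing data is 0.1856.
- Fitted dispersion falls from 1.20 (complete data) to 0.97.
- Imputation that uses the child's history gives SE 0.1914 against SD 0.1911, with coverage 94.9%.
- With no true effect, two-sided type I error is 6.3% for the PMM and 5.2% with history.

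PMM ratio of SE to sampling SD in other scenarios:

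| Dispersion | Withdrawn | Ratio |
|---|---|---|
| 0.5 | 20% | 0.975 |
| 2.5 | 20% | 0.96 |
| 1.5 | 10% | 0.975 |
| 1.5 | 30% | 0.92 |

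Tipping point, with odds multiplied and divided by 1.5 in the base case: ratio 0.95 to 0.96. Control-based: SE 0.1805 against SD 0.1597, a ratio of 1.13 (1.05 with no true effect).

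**Rate ratio when exacerbating children withdraw more often** (k = 1.5):

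| Arm affected | True RR | Complete data | Primary | PMM | With history |
|---|---|---|---|---|---|
| Placebo | 0.5 | 0.527 | 0.531 | 0.564 | 0.538 |
| Placebo | 1 | 1.009 | 1.020 | 1.080 | 1.030 |
| Both | 0.5 | 0.523 | 0.523 | 0.530 | 0.527 |
| Dupilumab | 0.5 | 0.521 | 0.514 | 0.485 | not run |

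On the log scale the PMM shift is ln(0.564/0.527) = +0.07 for placebo and ln(0.485/0.521) = −0.07 for dupilumab. The dupilumab row is a separate run of 400 trials with deliberately strong event-driven withdrawal: 0.8% per month, plus 25 percentage points after an exacerbation month. With no true effect under that pattern, the PMM rate ratio was 0.89 and wrongly favoured dupilumab in 12% of trials, against 1.3% for the primary analysis (nominal 2.5%). Another simulation, with about 18 to 21% withdrawn, gave the same directions: 0.60 against 0.52 with complete data (placebo) and 0.50 against 0.53 (dupilumab).

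**The case against.** - **The prior-year count is in every model.** A reader might infer that frequent exacerbators and non-exacerbators always get the same imputed rate. They do not: the prior-year count carries part of each child's tendency. The rates coincide only at equal baseline covariates.
- **The size may be at the low end.** Suppose 1.5 is the total dispersion and the prior-year count shares the same frailty. Entry requires at least one prior-year event (protocol section 7.1), so residual dispersion would be at most 1/(1/1.5 + 1) = 0.6, and at 0.5 the shortfall is 2.5%. Children who stop treatment are asked to stay in follow-up, so missing time may be below plan; at 10% withdrawn the shortfall is also 2.5%. The protocol allows a controller step-up after two severe exacerbations, so a constant underlying rate is itself an approximation. All of this stands, and it limits the size without removing the fault.
- **The bias is conservative.** This is true only when placebo children leave after exacerbating. When dupilumab children do so, the bias favours the drug. If both arms behave alike, it is small.
- **These analyses are supportive.** They lie outside the testing hierarchy, and the control-based and tipping-point versions depart from missing-at-random on purpose. This stands, and it is why the point does not touch the primary conclusion.
- **A simple repair brings problems.** An unrestricted negative binomial draw would break the limit of one event per 28 days. Monthly models are already sparse: about 115/13 + 230 × 0.5/13 = 17.7 events a month for nine slopes. Both points stand and shape the fix.

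**Conclusion.** The fault is in the stated rule: no exacerbation imputation model uses on-study events, and missing months are drawn independently. Under the superseded planning values, the PMM and tipping-point standard errors are about 5% too small. For the PMM the shortfall is about 2.5 to 8% over dispersion 0.5 to 2.5 and withdrawal 10 to 30%. The PMM even reports a smaller standard error than the same trial with no missing data. Withdrawal that follows exacerbations in one arm biases the imputed rate ratio, against dupilumab if that arm is placebo and in its favour if it is dupilumab.

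A reader might infer two stronger things that the documents and the check do not support:

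- **That all three checks understate their standard error.** The control-based one does not against its own sampling SD, although its SE is 5 to 6% below that of a version using history (0.1805 against 0.1925; 0.1683 against 0.1772 with no true effect).
- **That the primary result is compromised.** It does not impute.

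The sizes depend on redacted inputs, on the dispersion left after covariates and on how many children leave the study. The sponsor should correct this, because these analyses are the planned missing-data evidence for the primary endpoint.

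**What to change.** In Appendix D, keep the monthly Bernoulli structure, so that no child has more than one event per 28 days, and impute months in sequence. From Month 2, add the child's running on-study event count and time at risk (observed, then imputed) as covariates; Month 1 keeps the baseline covariates only. Fit one model pooled over months with a month term, to avoid sparse monthly fits.

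Carry this into the control-based and tipping-point versions. For the control-based version, state how a dupilumab child's history enters a placebo-fitted model. The COVID-19 imputation in section 2.4.4.1 is described as similar to the PMM, so it should follow the same rule. A negative binomial draw conditional on the child's own count and time is an alternative if the 28-day limit is kept.

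The cost is SAP wording and slightly more complex imputation code. No new data are needed.

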For each patient with partial missing data of severe exacerbation events, the unobserved number of events after study discontinuation up to Week 52 will be imputed on monthly basis. Since the definition of severe exacerbation in [Section 2.1.3.1](#) requires the start dates of 2 consecutive severe exacerbation events experienced by one patient to depart at least 28 days from each other, each patient is possible to have a maximum of one event per month that is defined as 28 days. A logistic regression model therefore can be used to impute whether a patient has an event or not for each of the corresponding unobservable months. This imputation will be repeated multiple times. A final statistical inference will be obtained by using Rubins' formula to combine the binomial regression results based on each of the imputed datasets. Details of the PMM model are described in [Appendix D](#).

- *Control-based PMM*

Similar to aforementioned PMM model except that the individual monthly mean probability will be calculated based on observations in placebo arm only in the logistic regression, with adjustment of missing observation duration.

- *Tipping point analysis*

Similar to aforementioned PMM model except that if a patient with missing data is on dupilumab, the odds in the logistic model for each unobservable month will be increased, and vice versa if the patient is on placebo, the odds will be decreased. This adjustment will artificially lower the predicted event rates in placebo group and increase the predicted event rates in Dupilumab group. For each increasing/decreasing ratio, a p-value can be obtained based on the imputed dataset with this specific ratio. A sequence of different ratios will be explored until p-value becomes >0.05 .

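### SAP Appendix D discards event-free days in the withdrawal month and redraws the whole month, a small upward bias confined to the missing-data sensitivity analyses

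*SAP*

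**What the plan says.** Three missing-data sensitivity analyses of the primary endpoint (pattern mixture model, control-based version, tipping point) share one imputation scheme, set out in SAP section 2.4.4.1 and Appendix D. A COVID-19 analysis in section 2.4.4.1 uses a similar one.

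- Step 1: "The 52-week observation period is partitioned into monthly (4-week) segments", which gives 13 months. Section 2.4.4.1 justifies a yes/no outcome per month from the 28-day separation rule: "each patient is possible to have a maximum of one event per month that is defined as 28 days".
- Step 2: within each month "the logistic regression model will be fitted to the observed data", giving each child a monthly event probability.
- Step 3 splits withdrawal on day k of Month i by outcome. If the child withdrew "and experienced a severe exacerbation within the first k days", Month i counts as observed and imputation starts at Month i+1. If the child withdrew "and has no severe exacerbation in Month i", the child is observed only to Month i-1 and imputation starts at Month i itself.
- For each imputed month, "40 independent random samples will be respectively drawn from 40 estimated Bernoulli distributions, whose probabilities are obtained in Step 2".
- Step 4: "log transformed 52 weeks will be the offset variable for patients who discontinue the study".

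Neither the text nor the sample PROC MI code scales the Step 2 probability to the 28-k days that were not seen. For the control-based version, section 2.4.4.1 and Appendix D mention an adjustment for the length of the missing observation. It is attached to Step 2 and is not defined.

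**The concern.** Whether the withdrawal month is retained depends on its outcome. A child with an event by day k keeps it. A child followed event-free for, say, 27 days loses those days and gets a fresh full-month chance of an event. Because the offset is 52 weeks either way, the redrawn days add no exposure, so the rule can only push imputed counts up.

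The primary analysis treats the same days differently. Under SAP section 2.4.4.1 observation time runs to the last contact date, so event-free days before withdrawal count as event-free time. The sensitivity analyses are meant to test the primary result against missing data, yet they also throw away data that were observed.

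A secondary effect follows in Step 2: withdrawal months enter the monthly fits only when they hold an event, which raises the fitted probabilities slightly.

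**Working it through.** **Inputs**

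- 13 segments of 28 days, at most one event each, full-month draw, 52-week offset (SAP Appendix D and section 2.4.4.1).
- 20% linear discontinuation at one year, mean exposure 0.9 year (SAP section 1.3).
- Event rates of 1.0 (placebo) and 0.5 (dupilumab) per year, with dispersion 1.5. These come from the superseded sample-size text in SAP section 1.5, because current values are redacted. They serve only as an anchor.
- Assumptions: withdrawal day uniform on k = 1 to 27, unrelated to events; constant hazard within the month.

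**Anchor check.** The documents give no figure for the withdrawal-month probability. The superseded sample size does reproduce. SE of the log rate ratio = sqrt[(1/(0.9×1.0)+1.5)/98 + (1/(0.9×0.5)+1.5)/196] = 0.214. Then ln 2/0.214 - 1.96 gives power of about 90% with 294 patients, as stated.

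**Withdrawal month.** Let p = 1-exp(-rate×28/365.25) be the full-month probability and q_k = 1-(1-p)^(k/28) the chance of an event by day k. Under the written rule the month's event probability is

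q_k + (1-q_k)p = 1-(1-p)^(1+k/28),

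which exceeds p for every k. The coherent value is p.

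| Rate per year | p | Rule, mean over k | Excess | Relative |
|---|---|---|---|---|
| 1.0 | 0.0738 | 0.1084 | 0.0346 | +47% |
| 0.5 | 0.0376 | 0.0558 | 0.0182 | +48% |

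At 1.0 per year the inflation by day is +3% (k=1), +24% (k=7), +47% (k=14), +70% (k=21) and +89% (k=27). Over rates of 0.25 to 3 per year the average runs from about +49% down to about +40%. A simulation with 20% uniform dropout and dispersion 0 or 1.5, re-estimating p from the months flagged as observed, gave +46% to +50%.

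**Arm rates, standard pattern mixture model, 20% withdrawal**

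- Placebo: 0.2×0.0346/(13×0.0738) = 0.72%.
- Dupilumab: 0.2×0.0182/(13×0.0376) = 0.74%.
- Rate ratio: multiplied by 1.0074/1.0072, so 0.500 becomes about 0.5001.

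**Control-based version, 20% withdrawal, if its duration adjustment does not reach Step 3.** A dupilumab child is redrawn at the placebo probability.

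- Mean of q_k(0.5) + (1-q_k(0.5))×0.0738 is 0.0913.
- Drawing only the remaining 28-k days at the placebo hazard gives 0.0558, so the excess is 0.0355.
- With 10% of follow-up imputed, the dupilumab mean is 13×(0.9×0.0376+0.1×0.0738) = 0.536, and 0.2×0.0355/0.536 = 1.3%.
- Rate ratio: 1.013/1.007, a shift of about +0.6%.

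**Unequal withdrawal (illustrative, 10% placebo and 30% dupilumab)**

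- Standard: 0.1×0.0346/0.959 = 0.36% and 0.3×0.0182/0.489 = 1.12%, a ratio shift of about +0.75%.
- Control-based: the dupilumab mean is 13×(0.85×0.0376+0.15×0.0738) = 0.559, and 0.3×0.0355/0.559 = 1.9%, a ratio shift of about +1.5%.
- With the percentages reversed, the shifts are about -0.7% and -0.4%.

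**Step 2 fits.** With w = 0.2/13 = 0.0154 withdrawing per month and mean q_k of 0.0376 at 1.0 per year, the fitted value is [0.0738(1-w)+0.0376w]/[(1-w)+0.0376w] = 0.0743. That is about 0.7% above p; the simulation gives about 0.8%. It acts only on imputed time, about 10% of follow-up, so it adds under 0.1% to an arm's rate.

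**The case against.** The strongest reply is that nothing of consequence moves. The target is a rate ratio, and with balanced withdrawal the standard analysis leaves it at 0.5001 instead of 0.500. Even the +1.5% shift under strongly unequal withdrawal is about 0.015 on the log scale, against a standard error near 0.21, or roughly 7% of one standard error. The tipping point analysis deliberately moves the odds much further. This stands, and it limits the weight of the point.

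The 20% is also a planning figure for discontinuation. Only study withdrawal triggers imputation, and children who stop treatment are encouraged to stay to Week 52. Actual imputation may be lower, and the effect falls in proportion.

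A reader might infer that every missing-data analysis is certainly biased. The documents do not support that for the control-based version, because its undefined duration adjustment may deal with the problem. As written, though, it sits in Step 2 and not in the Step 3 draw.

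Finally, PROC MI by month draws at the fitted full-month probability, so a day-specific draw needs extra code and its own constant-hazard assumption. Restricting the Step 2 fit to fully followed months would discard real events, and could bias p downward if children tend to withdraw after an exacerbation. Both remarks are fair. The second is why the Step 2 change is only optional.

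**Conclusion.** The rule as written is biased upward, and the bias follows from the text whatever the event rate. In the withdrawal month it averages about 47% at 1.0 event per year and 48% at 0.5, on the stated assumptions of a uniform withdrawal day, constant hazard and superseded planning rates.

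A reader might take that figure as inflation of the trial's event rate or of the treatment effect. The documents do not support this. It concerns one month of 13, only in children who withdraw, and only in the pattern mixture, COVID-19 and tipping point analyses, plus the control-based one unless its adjustment corrects it. The primary analysis performs no imputation. At 20% withdrawal the cost is about 0.7% on each arm's rate in the standard analysis. The rate-ratio shift runs from negligible to about 1% to 2% across the settings examined. This is a minor correction, worth making because the bias is avoidable and uses data already in hand; it is unlikely to alter any conclusion.

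**What to change.** In Appendix D Step 3, for a child event-free to day k of Month i, draw Month i with probability 1-(1-p)^((28-k)/28) and later months with p as now. In practice, let PROC MI draw Month i as planned and then retain a drawn event with probability about (28-k)/28. At p = 0.0738 and k = 14 the exact retention probability is 0.51, against 0.50 from this shortcut. In the simulation the remaining-days draw, run together with a Step 2 fit on fully followed months, brought the withdrawal-month inflation to within about 1% of zero.

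State that the same draw applies to the control-based, tipping point and COVID-19 versions, and either define the control-based duration adjustment or replace it with this rule.

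Fitting Step 2 only to fully followed months is optional, given its effect of under 0.1% on the rate and the loss of real events.

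The cost is a short data step after the sample PROC MI code, the withdrawal day carried in the imputation dataset, and an explicit assumption of constant hazard within a month. No new data are needed.
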